**Table 11 Definition of CTCAE Grades 0-4** 

Laboratory data	Grade 0	Grade 1	Grade 2	Grade 3	Grade 4
ALT	<=ULN	>ULN – 3 x ULN	> 3 – 5 x ULN	> 5 – 20 x ULN	> 20 x ULN
AST	<=ULN	>ULN – 3 x ULN	> 3 – 5 x ULN	> 5 – 20 x ULN	> 20 x ULN
Hemoglobin Decreased [g/L]	>=130	<130 – 100	< 100 - 80	< 80 - 65	< 65
Creatinine Clearance[mL/min]	>= 75	< 75 - 60	< 60 - 30	< 30 – 15	< 15

Table 12 Overview of Outputs for Safety Variables

Output Title	Output Short Name	Analysis Population
Exposure to Study Medication by Treatment Regimen and Cirrhosis Status - SP - <country></country>	tesm_ <c>_tc_sp</c>	Safety population
Unintended Medication Error/ Pregnancy by Treatment Regimen and Cirrhosis Status — SP - <country></country>	tum_ <c>_tc_sp</c>	Safety population
Treatment-emergent AEs by Treatment Regimen and Cirrhosis Status - SP - <country></country>	tae_ <c>_tc_sp</c>	Safety population
Serious Treatment-emergent AEs by Treatment Regimen and Cirrhosis Status - SP - <country></country>	tsae_ <c>_tc_sp</c>	Safety population
Non-Serious Treatment-emergent AEs by Treatment Regimen and Cirrhosis Status - SP - <country></country>	tnsae_ <c>_tc_sp</c>	Safety population
Treatment-emergent AEs by Severity by Treatment Regimen and Cirrhosis Status - SP - <country></country>	taes_ <c>_tc_sp</c>	Safety population
Treatment-emergent AEs Leading to Death by Treatment Regimen and Cirrhosis Status - SP - <country></country>	taed_ <c>_tc_sp</c>	Safety population
Treatment-emergent AEs Leading to Hospitalization by Treatment Regimen and Cirrhosis Status - SP - <country></country>	taeh_ <c>_tc_sp</c>	Safety population
Treatment-emergent AEs Possibly Related to ABBVIE Regimen by Treatment Regimen and Cirrhosis Status - SP - <country></country>	taera_ <c>_tc_sp</c>	Safety population
Treatment-emergent AEs Possibly Related to Ribavirin in Patients taking RBV by Treatment Regimen and Cirrhosis Status - SP - <country></country>	taerr_ <c>_tc_sp_RB V</c>	Safety population: patients taking RBV
Treatment-emergent AEs Caused by Medication Error - Paritaprevir/r-Ombitasvir - by Treatment Regimen and Cirrhosis Status - SP - <country></country>	taempo_ <c>_tc_sp</c>	Safety population
Treatment-emergent AEs Caused by Medication Error - Dasabuvir - in Patients taking 3DAA by Treatment Regimen and Cirrhosis Status - SP - <country></country>	taemd_ <c>_tc_sp_3d aa</c>	Safety population: patients taking 3DAA
Treatment-emergent AEs Leading to Withdrawal of ABBVIE Regimen by Treatment Regimen and Cirrhosis Status - SP - <country></country>	taewa_ <c>_tc_sp</c>	Safety population
Treatment-emergent AEs Leading to Withdrawal of Ribavirin in Patients taking RBV by Treatment Regimen and Cirrhosis Status - SP - <country></country>	taewr_ <c>_tc_sp_RB V</c>	Safety population: patients taking RBV
Listing of SAEs - SP - <country></country>	lsae_ <c>_sp</c>	Safety population
Glossary for AEs - <country></country>	tgae_ <c></c>	-
Co-medication by Treatment Regimen and Cirrhosis Status - SP - <country></country>	tcom_ <c>_tc_sp</c>	Safety population
Co-medication by Profile and by Treatment Regimen and Cirrhosis Status - SP - <country></country>	tcomp_ <c>_tc_sp</c>	Safety population
Associated Treated Condition by Treatment Regimen and Cirrhosis Status - SP - <country></country>	tatc_ <c>_tc_sp</c>	Safety population
Associated Treatment Profiles by Medication of Special Interest and by Treatment Regimen and Cirrhosis Status - SP - <country></country>	tatp_ <c>_mtc_sp</c>	Safety population

Glossary for Co-medication - <country></country>	tgcom_ <c></c>	-	
Laboratory Hematology by Treatment Regimen and Cirrhosis Status - SP - <country></country>	tlh_ <c>_tc_sp</c>	Safety population	
Laboratory Clinical Chemistry by Treatment Regimen and Cirrhosis Status - SP - <country></country>	tlc_ <c>_tc_sp</c>	Safety population	
CD4 and HIV RNA in Patients With HIV by Treatment Regimen and Cirrhosis Status - SP - <country></country>	tlch_ <c>_tc_sp_hiv</c>	Safety population	
Potentially Clinically Significant Laboratory Values by Treatment Regimen and Cirrhosis Status - SP - <country></country>	tpcs_ <c>_tc_sp</c>	Safety population	
Worst Laboratory Values by Treatment Regimen and Cirrhosis Status - SP - <country></country>	twlv_ <c>_tc_sp</c>	Safety population	

The layouts of the tables mentioned above are provided in Part II of the SAP (Table Shells).

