9.7.4 Clinical Laboratory Data

All reported clinical laboratory test results will be assigned to one of the time points using the time windows specified in the table below.

Table 4 - Analysis Time Windows

Phase	Time point	Time Window
Pre-Treatment	Baseline	Last value prior to start of study treatment (i.e. ≤study day 1)
Treatment Weeks	4 (day 29)	Study day during treatment period (Study day 1 = first treatment day) 15 - 42
	8 (day 57)	43 - 70
	12 (day 85)	71 - 98
	16 (day 113)	99 - 126
EoT	Actual EoT	Study day of last dose (28 days prior to EoT - 14 days post EoT)
Post Treatment	4 weeks (day 29 post EoT)	15 – 56 post EoT
	12 weeks (day 85 post EoT)	57 – 112 post EoT
	24 weeks (day 169 post EoT)	141 – 196 post EoT

Mean changes from baseline to each post-baseline visit will be summarized descriptively.

Laboratory data values collected during the treatment period will be categorized as low, normal, or high based on reference ranges used in this study. The number and percent of patients who experience post-baseline shifts during treatment in clinical laboratory values from low/normal to high and high/normal to low based on the reference range will be summarized.

Confidential Information

No use or disclose outside AbbVie is permitted without prior written authorization from AbbVie

Additional details of the analyses of clinical laboratory data will be specified in the SAP.

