#### 4.2.8.4 Laboratory Data

All reported clinical laboratory test results will be assigned to one of the time points using the time windows specified in the Table 4. All will be performed for the SP by treatment regimen and cirrhosis status.

Changes from baseline to each post-baseline visit will be summarized descriptively (N, mean, SD, median, minimum, maximum). A summary table will show laboratory hematology. In another table, information about clinical chemistry will be summarized.

In a further table CD4 and HIV-RNA are displayed for patients with HIV only by visit.

Instead of the shift tables mentioned in the study protocol, the number and percentage of subjects with post-baseline values until EoT meeting the specified criteria for Potentially Clinically Significant (PCS) laboratory values (defined in Table 10) will be summarized. A post-baseline value must be more extreme than the baseline value to be considered a PCS finding.

Table 10 Criteria for PCS laboratory values

Laboratory data	Very Low	Very High
Laboratory hematology		
Hemoglobin [g/L]	<80	
Platelets [10  /L]	<50	
Laboratory clinical chemistry		
ALT		>5 x ULN and >= 2 x baseline
AST		>5 x ULN and >= 2 x baseline
Creatinine [µmol/L]		>132.605
Creatinine clearance [mL/min]***	<50	

\*\*\* estimated by Cockcroft-Gault-Formula (see above)

Additionally, for hemoglobin and creatinine clearance, the number and percentage of subjects with a maximum Common Terminology Criteria for Adverse Events (CTCAE) Grade of 0, 1, 2, 3, or 4 (see definitions in Table 11) at any post-baseline visit (regardless of the baseline value) through the end of treatment (i.e., Final Treatment Value) will be summarized. For the liver function tests (LFTs) of ALT and AST, the number and percentage of subjects in with a maximum CTCAE Grade of 0, 1, 2, 3, or 4 (see definitions in Table 11) at any post-nadir visit through the end of treatment (i.e., Final Treatment Value) will be summarized. Note, for these analyses, the nadir is used for reference (including baseline).

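### SAP Table 11 grades haemoglobin against one 130 g/L limit for both sexes and ignores baseline, so unchanged values of 100 to <130 g/L are counted as Grade 1 decreases

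*SAP*

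**What the plan says.** SAP Table 11 gives one haemoglobin row, "Hemoglobin Decreased [g/L"], in g/L: Grade 0 at 130 or above, Grade 1 from 100 to below 130, Grade 2 from 80 to below 100, Grade 3 from 65 to below 80, Grade 4 below 65. The limits are not split by sex and not tied to a laboratory lower limit.

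The rule for using the table is in SAP 4.2.8.4: "Additionally, for hemoglobin and creatinine clearance, the number and percentage of subjects with a maximum Common Terminology Criteria for Adverse Events (CTCAE) Grade" of 0 to 4 are reported, the grade being the worst one reached "at any post-baseline visit (regardless of the baseline value) through the end of treatment".

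The same section treats other laboratory counts differently:

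- For ALT and AST, limits are multiples of the upper limit of normal, and "Note, for these analyses, the nadir is used for reference (including baseline").
- For potentially clinically significant (PCS) values, where the haemoglobin criterion is below 80 g/L (Table 10), "A post-baseline value must be more extreme than the baseline value to be considered a PCS finding".

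On stratification, the section says "All will be performed for the SP by treatment regimen and cirrhosis status". Sex is not a stratum.

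Protocol 9.7.4 had planned that on-treatment values would be "categorized as low, normal, or high based on reference ranges used in this study", with counts of post-baseline shifts. SAP 4.2.8.4 says openly that the PCS summary replaces the shift tables.

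**The concern.** The row is labelled as a decrease, but the rule measures the level reached, not a change. A value that never moves can be graded as decreased. The Grade 0/1 limit is also the same for men and women, so a woman inside her normal range can be placed in Grade 1.

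Describing tolerability is a secondary objective in both documents. Protocol 7.1 says many adverse events and laboratory abnormalities in Phase III were attributable to ribavirin, and anaemia is a listed reason for stopping or modifying ribavirin in SAP 4.2.5 and 4.2.7.2.1. Haemoglobin grade by regimen is thus a table that readers will use to compare groups with and without ribavirin. If Grade 1 mixes new falls with values already low at baseline and with normal female values, that comparison is hard to read.

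**Working it through.** The plan states no figure on this point, so there is nothing to reproduce. The check applies the rules as written and then sizes the effect on assumed inputs.

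**Step 1. Apply Table 11 to unchanged values.** Values of 118, 120, 122, 125, 128 and 129 g/L, the same at baseline and at every visit, all give Grade 1. Values of 130 and 135 g/L give Grade 0. This holds for both sexes.

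**Step 2. Ask whether another laboratory count separates stable from falling patients.** The patients below are illustrative; only the rules come from the SAP.

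| Baseline (g/L) | Worst on treatment (g/L) | Change | Table 11 grade | PCS (<80 and worse than baseline) |
|---|---|---|---|---|
| 125 | 125 | 0 | 1 | No |
| 135 | 100 | -35 | 1 | No |
| 80 | 80 | 0 | 2 | No |
| 135 | 80 | -55 | 2 | No |

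Within each pair, the stable and the falling patient are counted identically. The 130 g/L limit matters only for the Grade 0/1 split, but ignoring baseline affects every grade.

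**Step 3. Size of the sex effect (illustrative).** The documents give no female reference range, haemoglobin distribution or sex ratio. Assume a normal distribution for women and take the share between the lower limit of normal (LLN) and 130 g/L:

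share = Φ((130 − mean)/SD) − Φ((LLN − mean)/SD)

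- Central case, mean 135, SD 10, LLN 120: Φ(−0.5) − Φ(−1.5) = 0.309 − 0.067 = 0.242.
- Lowest case in the grid (mean 130 to 140, SD 8 to 12, LLN 115 to 125): mean 140, SD 8, LLN 125 gives 0.075.
- Highest case: mean 130, SD 8, LLN 115 gives 0.470.

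The range is therefore about 8% to 47% of women. With the planned 400 patients and an assumed 40%, 50% or 60% women, the central case gives 400 × 0.4 × 0.242 = 39, 400 × 0.5 × 0.242 = 48, or 400 × 0.6 × 0.242 = 58 patients in Grade 1 with a normal value. This describes a single reading. The table takes the worst of several readings, which can only hold the grade or raise it.

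**Step 4. Sex mix between regimens.** In the central case, a group with 40% women carries 0.4 × 0.242 = 9.7% from this source, and a group with 60% women carries 0.6 × 0.242 = 14.5%. The 4.8-point difference involves no drug effect.

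**The case against.** The best defence is that the table does what its name in SAP Table 12 says: it reports worst laboratory values. The clause on baseline in 4.2.8.4 is explicit, so the choice is declared. Replacing the shift tables is also disclosed, and Protocol 9.7.4 leaves further laboratory detail to the SAP. That stands, so this is not a hidden contradiction between the documents. The row label still says decreased, and the count it gives is not one of decreases.

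A reader might go further and infer that no output can separate treatment-related falls from baseline status, or that tolerability cannot be described at all. The documents do not support either. SAP 4.2.8.4 summarises change from baseline at each visit with mean, SD, median, minimum and maximum. Treatment-emergent adverse events are tabulated by severity and by relation to ribavirin, and ribavirin modification or termination for anaemia is reported. Baseline haemoglobin is tabulated for the safety population by the same regimen and cirrhosis strata. What is missing is narrower: a laboratory count of patients with a new mild or moderate fall.

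A reader might also think that cirrhosis mix distorts the grade rates. The tables are already split by cirrhosis status, so within those rows it does not. Sex mix is the factor left open. Gender is tabulated by the same strata, which helps a careful reader but does not correct the grade counts. No formal comparison of laboratory grades between regimens is planned.

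Finally, the size rests wholly on assumed values, and the Part II table shells were not available. A baseline column there cannot be ruled out, but the SAP text mentions none.

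**Conclusion.** The point holds in a limited form. It follows from the text alone, with no assumption, that any patient with an unchanged haemoglobin of 100 to <130 g/L is counted as Grade 1 decreased, and that no laboratory patient count in the SAP text identifies new falls that stay at or above 80 g/L.

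That some of these patients are women with normal values needs one assumption: a female lower limit below 130 g/L. It would not be right to say that all women with normal haemoglobin are misgraded; only those between their lower limit and 130 g/L are. The 8% to 47% range and the 39 to 58 patients are illustrations, not estimates for this study.

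The consequence is confined to one descriptive safety table. SVR12, the analysis populations, the PCS counts and the mean changes are untouched. The change is worth making because it costs little and makes the haemoglobin grades usable for the tolerability objective.

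**What to change.** 1. In SAP 4.2.8.4, for haemoglobin, cross-tabulate worst on-treatment grade by baseline grade, with a row for missing baseline. Alternatively, count only grades worse than the baseline grade, in line with the PCS rule. The cross-tabulation shows more. Do the same for creatinine clearance, which falls under the same rule that ignores baseline.
2. In Table 11, state one Grade 0/1 haemoglobin limit per sex. A fixed value per sex is needed because Protocol 9.4.1.1 to 9.4.1.3 list upper limits for ALT and AST but no lower limit for haemoglobin, and Protocol 9.6.1 restricts the eCRF to data specified in the protocol. A rule based on the local laboratory limit may therefore not be feasible.

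The first change settles the baseline problem for both sexes even if the single 130 g/L limit is kept. The second alone does not.

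The cost is one table row, one derivation and one revised shell. Sex and baseline haemoglobin are already collected. One limitation remains: a fall within a grade, such as 129 to 100 g/L under the present limits, would still show no worsening, so the change-from-baseline summary should stay. A small downside is that Grade 0/1 counts may differ from those of other studies that used the single limit.

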## 4.2.9 Interim Analyses

One interim analysis is planned. It will be performed in the first quarter of 2017.

All analyses described above will be performed, but the populations will be restricted to patients who started treatment before 1st April 2016 and with a planned treatment duration of 12 weeks.

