Univariate and multiple logistic regression (MLR) methods will be used to investigate the impact of various explanatory covariates (e.g. demographic and disease characteristics, co-morbidities, type of treating institution, and prior treatment for CHC and response outcome in treatment experienced patients) on SVR12. These analyses will be of exploratory nature, data driven, and will be performed for various CP analysis groups since not each covariate might be predictive in each patient group. Furthermore, the fact that treatment regimens will differ in the various patient groups has to be taken into account, when selecting the patient groups for each MLR analysis. Backward selection procedures will be applied to generate the final MLR models which will consider only covariates in the selection procedure with a p-value <0.25 in the corresponding univariate logistic regression analysis. A p-value <0.05 will be used for the covariates to stay in the model in a backward elimination step. Logistic regression methods will also be used to investigate the impact of treatment adherence on SVR12.

All safety variables will be summarized for patients in the SP using descriptive statistical methods stratified by the type of combination treatment and scheduled treatment duration.

Milestones:

Start of Data Collection:	October 2015
End of Data Collection for Interim Analysis:	December 2016
End of Data Collection for Final Report:	March 2017
Interim Analysis of Study Results:	March 2017
Final Report of Study Results:	June 2017

Confidential Information

No use or disclose outside AbbVie is permitted without prior written authorization from AbbVie

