**Table 2 - Data Documentation Schedule** 

Assessment/ Procedure		Treatment Period		Post-treatment (PT) Period			
(only available data to be collected; no diagnostic or monitoring procedures to be applied to the patients apart from those of routine clinical practice)	Baselin	On- treatment visits	Mid treatment visit for pts receiving 24 weeks of therapy	EoT b	Early PT visit	SVR 12 visit	SVR 24 visit
Patient authorization	X a						
Demographic information	Χ						
IL28B	Χ						
Relevant CHC disease characteristics	Х						
Liver fibrosis stage	Х						
CHC treatment history	Χ						
HCV genotype and subtype	Χ						
HCV RNA samples	Х	Х	Х	Х	Х	Χ	Χ
Clinical chemistry and hematology	Χ	Х	Χ	Х	Х	Х	Х
ABBVIE REGIMEN initiation documentation	Х						
ABBVIE REGIMEN adherence		Х	Χ	Х			
Concomitant medication	Χ	Х	Χ	Χ			
Relevant medical history, co-morbidities	Χ						
sAE, AE and pregnancy reporting	Х	Х	Х	Х	Xc	$X_q$	Xd
For patients receiving RBV: Evidence, in accordance with local label, that female patient or female partner of male patient is not pregnant	Х						
Patient questionnaires – WPAI, EQ5D-5L	Χ			Х		X	Х

Abbreviations: EoT = End of Treatment (at Week 12 or 24 or at premature discontinuation), PT = Post-Treatment

- a Written patient authorization must be obtained before any data documentation in the eCRF
- b Patients who prematurely discontinue should return to the site to document EoT data
- c Tolerability documentation until PT week 4
- d Pregnancy reporting for patients treated with DAA plus RBV

In accordance with the non-interventional nature of the study all HCV RNA measurements will be performed at the sole discretion of the physician and all HCV RNA measurements have to be entered into the eCRF. All recorded HCV RNA values will be assigned to appropriate time points (baseline, on-treatment visits, EoT visit, post-treatment visits) as follows:

Table 3 - Analysis Time Windows for HCV RNA

Phase	Time point	Time Window
Pre-Treatment	Baseline	Last value prior to start of study treatment (i.e.
		≤study day 1)
On-treatment		Study day during treatment period^#
		(Study day 1 = first treatment day)
Treatment Week	4 (RVR*)	15 - 42^
EoT	Actual EoT	Study day of last dose#
		(28 days prior to last dose - 7 days post last
		dose)
Post Treatment	12 weeks (SVR 12	>=70-126 days post last dose
	window)	
	24 weeks (SVR24	127-210 days post last dose
	window)	

^values must also be <= 7 days post last dose

#>=study day 2

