# 4.2.3 Handling of missing data

No data will be imputed for any effectiveness or safety analyses except for the analyses of the HCV RNA endpoints and certain PRO endpoints. The discussion of missing data imputation for the PRO endpoints is included in section 4.2.7.2.3.

HCV RNA values will be selected for an RVR, EOTR and SVR analysis based on visit windows as defined in Table 3. When there is no HCV RNA value in a visit window based on defined visit windows, the closest values before and after the window, regardless of the value chosen for the subsequent and preceding window, will be used for the flanking imputation described below. For analysis of RVR, EOT and SVR, if a subject has a missing HCV RNA value at a post-Day 1 visit but with undetectable or unquantifiable (≤50 IU/mL) HCV RNA levels at both the preceding value and succeeding value, the HCV RNA level will be considered undetectable or unquantifiable,

respectively, at this visit for this subject. In addition, if a subject has an unquantifiable HCV RNA level at the preceding value and an undetectable HCV RNA level at the succeeding value, or vice versa, the HCV RNA level will be imputed as unquantifiable at this visit for this subject.

For analyses of RVR, subjects still missing a value for the visit after flanking imputation will be imputed as a failure. For EoTR and SVR analysis, if there is no value in the appropriate window after flanking imputation but there is an HCV RNA value after the window, then it will be imputed into the EoTR or SVR window respectively. Subsequent to this flanking imputation, if a subject is missing a value for the visit window associated with the analysis, the subject will be imputed as a visit failure (i.e., not undetectable or unquantifiable).

If a subject starts another treatment for HCV, then all HCV RNA values for this subject measured on or after the start date of the new HCV treatment will be excluded from analyses. The subject will be considered a failure for summaries of viral response at all time points after the start of the new HCV treatment.

Due to the non-interventional nature of this study several different methods for determination of the HCV RNA value can be applied. For the purpose of the statistical analysis, a HCV RNA measurement is considered ≤50 IU/mL.

- if a PCR test was used

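### Interim SVR24 regressions: patients still untested inside an open window at a December 2016 cut are scored as failures

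*SAP*

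**What the plan says.** - **Scope of the interim (SAP 4.2.9).** "All analyses described above will be performed, but the populations will be restricted to patients who started treatment before" 1 April 2016 "and with a planned treatment duration of 12 weeks". On timing: "It will be performed in the first quarter of 2017". The SAP gives no data cut-off date.
- **Data cut (Protocol 4.0, Milestones).** The milestone "End of Data Collection for Interim Analysis" is set at December 2016, with no day. Interim results are due in March 2017. Protocol 6.0 lists December 2016 as the end of data collection and does not mention the interim.
- **Windows (SAP 4.2.2, Table 3).** SVR12 is ">=70-126 days post last dose" and SVR24 is "127-210 days post last dose". The day count is "Study day 1 = first treatment day".
- **Missing values (SAP 4.2.3).** A gap can be filled by flanking values, or by a value recorded after the window. Failing both, "if a subject is missing a value for the visit window associated with the analysis, the subject will be imputed as a visit failure".
- **Populations (SAP 4.2.1 and 4.2.7.2.1).** The SVR24 rate is reported in the core population with sufficient follow-up for SVR24 (CPSFU24). That set leaves out patients who were responders at their last test and have no test after day 126, when the reason is unrelated to safety or effectiveness. The SVR24 regressions on baseline covariates and on adherence are run in the CP, which has no follow-up requirement.

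**The concern.** The start-date limit makes the interim cohort old enough to reach the nominal 24-week visit by early December 2016. It does not make it old enough for the SVR24 window that the SAP itself defines. Follow-up visits and HCV RNA tests are left to routine practice, so some tests late in the window are to be expected.

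A patient whose window is open and who has not been tested at the cut has no succeeding value for flanking and no later value to carry back. The rule then makes that patient a failure. Nothing in the SAP separates a test still pending from a test that was missed. True failures are expected to be few, so a handful of false ones among the latest starters could change which covariates survive backward elimination at p<0.05. Interim and final regressions could then differ with no new virological failure.

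Adherence is exposed in a particular way. A patient who stops early has an earlier last dose, so the window closes sooner. Among late starters, the pending patients are therefore more often those who completed treatment.

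**Working it through.** **1. The plan's own figure.** The maximum observation period for a 12-week patient is 84 + 168 = 252 days = 36 weeks, as stated in SAP 3.1.

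**2. Dates for the latest eligible start, 31 March 2016.** With day 1 as the first treatment day, the last dose is start + 83 days.

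| Event | Days after last dose | Date |
|---|---|---|
| Last dose | 0 | 22 June 2016 |
| SVR12 window closes | 126 | 26 October 2016 |
| SVR24 window opens | 127 | 27 October 2016 |
| Nominal 24 weeks | 168 | 7 December 2016 |
| SVR24 window closes | 210 | 18 January 2017 |

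If treatment runs 7 days over, which the SAP still counts as not deviating, the window closes on 25 January 2017.

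**3. Who has an open window.** The window is closed at the cut if start ≤ cut − (83 + 210) = cut − 293 days. The documents give no day in December and no accrual curve. I assume uniform starts from 1 October 2015 (start of data collection) to 31 March 2016, which is 183 days.

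| Cut | Last start with closed window | Open start-days | Share of interim patients |
|---|---|---|---|
| 1 Dec 2016 | 12 Feb 2016 | 48 | 48/183 = 26% |
| 15 Dec 2016 | 26 Feb 2016 | 34 | 34/183 = 19% |
| 31 Dec 2016 | 13 Mar 2016 | 18 | 18/183 = 10% |

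**4. Who is still untested.** If tests fall evenly over the 84 days from 127 to 210, a start with k window days remaining is untested with probability k/84. For m open start-days the share is (1 + … + m)/84/183:

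- 1 December: 1176/84/183 = 7.7%
- 15 December: 595/84/183 = 3.9%
- 31 December: 171/84/183 = 1.1%

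**5. Sensitivity to the assumptions.**

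| Assumption | 1 Dec | 15 Dec | 31 Dec |
|---|---|---|---|
| Even over days 127–210, starts from 1 Oct 2015 | 7.7% | 3.9% | 1.1% |
| Same, starts only from 1 Jan 2016 (91 days) | 15.4% | 7.8% | 2.2% |
| Tests centred on day 168, SD 14 days, starts from 1 Oct 2015 | 5.1% | 1.4% | 0.1% |
| Even over days 127–168, starts from 1 Oct 2015 | 0.3% | 0% | 0% |

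For the last row at 1 December, only starts on 26–31 March count: (1 + … + 6)/42/183 = 0.3%.

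**6. Effect on the outcome variable.** Let p be the true SVR24 proportion and u the untested share from step 4. Assume that all true failures are already known. The regressions then see p(1 − u) successes, while the CPSFU24 rate is p(1 − u)/[p(1 − u) + 1 − p]. The plan gives no SVR24 rate, so its SVR12 planning values of 95% and 90% stand in for p.

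| Cut | u | p = 95%: regressions (CP) | p = 95%: CPSFU24 rate | p = 90%: regressions (CP) | p = 90%: CPSFU24 rate |
|---|---|---|---|---|---|
| 1 Dec | 7.65% | 87.7% | 94.6% | 83.1% | 89.3% |
| 15 Dec | 3.87% | 91.3% | 94.8% | 86.5% | 89.6% |
| 31 Dec | 1.11% | 93.9% | 94.9% | 89.0% | 89.9% |

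At p = 95% the false failures are 0.95 × u = 7.3%, 3.7% or 1.1% of patients, against 5% true failures.

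**7. Relapse in the SVR24 window.** The denominator needs EoT response, completed treatment, and a test at or after day 70 or an earlier post-treatment failure. A pending patient with an SVR12 test is in it and has no HCV RNA ≥50 IU/mL on record, so counts as a non-relapser. The same patient is a failure in the regression.

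**The case against.** Much of the case on the other side stands.

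- **The SVR24 rate.** A reader might infer that untested patients depress the reported interim SVR24 rate as failures. The documents do not support that. The rate is reported in CPSFU24. A pending test is not named among the exclusion reasons, but those are only examples, and it is unrelated to safety or effectiveness. What remains is a small downward bias, because known failures stay while pending responders leave.
- **Relapse.** A reader might also infer inflated relapse. Relapse needs a documented positive value, so the effect, if any, runs the other way.
- **The primary endpoint.** On schedule, every SVR12 window closes by 26 October 2016. The only route to an effect is a patient with no test in days 70–126 whose first later test falls after the cut. The documents give no basis for sizing this.
- **Planned observation.** Follow-up is capped at 24 weeks after treatment. By 15 or 31 December every on-schedule interim patient has passed the nominal visit, so only tests done late in the window are missed. This is why the share can be near zero.
- **The cut date.** December 2016 comes from the protocol. The SAP says only first quarter of 2017, and a snapshot from late January would remove the problem. One cannot say that the interim will certainly run on immature data.
- **Consequence.** The regressions are exploratory, and the documents attach no decision rule to the interim.

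These points do not reach the regressions. They use the CP, the failure rule applies there, and no stated cut-off prevents it.

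**Conclusion.** The point holds for the interim SVR24 baseline-covariate and adherence regressions. With a December 2016 cut, the SAP's rules turn some patients with an open window and no test yet into failures. The size depends on the cut day, accrual and test timing, and the documents state none of these. Under uniform starts from 1 October 2015 and evenly spread tests, 7.7%, 3.9% or 1.1% of interim patients are affected at a 1, 15 or 31 December cut. The share is close to zero at mid or late December if testing is done by day 168, and about double if starts were concentrated from January 2016.

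The primary SVR12 analysis is essentially untouched, the SVR24 rate is only slightly low, and the final analysis does not inherit an interim cut. Whether the non-core population response table shows SVR24 at the interim cannot be told, because the table shells are not in the documents. This is a minor, avoidable fault in an exploratory interim.

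**What to change.** State the interim HCV RNA cut-off date in SAP 4.2.9, bring the milestones in Protocol 4.0 and 6.0 into line with it, and add one of the following:

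1. Set the cut-off on or after 25 January 2017 (18 January plus the 7-day overrun). This is still in the first quarter of 2017 and closes every on-schedule window.
2. Limit the interim SVR24 regressions and, for consistency, the SVR24 rate and the relapse rate in the SVR24 window to patients whose last dose was at least 210 days before the cut-off.

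The first costs a few weeks. The second costs some patients in the interim SVR24 outputs: about 10% at a 31 December cut and 26% at a 1 December cut under the uniform-start assumption. It also lets in late starters who stopped early while leaving out those who completed. An equivalent start-date limit (for a 31 December cut, starts up to 13 March 2016) avoids that, so the later cut-off is the cleaner choice if the calendar allows it.
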